### 6.3.6 Summary of Baseline efficacy endpoints

A summary of baseline efficacy endpoints will be displayed for mMRC-10 sum score, mMRC-14 sum score, GS-daily average for the most affected hand and the less affected hand, GS 3 day moving average for the most affected hand and the less affected hand, MMN-RODS centile metric score, CAP-PRI total score and average FSS score.

## 6.4 Safety Evaluations

### 6.4.1 Adverse Events

All adverse events evaluations will be performed in the SAF set. For the DBTP period, TEAEs will be presented up V14 for participants who roll over to the LTE and for other participants through to the day before the first visit in the safety follow-up period (FUV1) or the date of last available data if FUV1 has not been attended.

AE onset and duration will be derived as follows:

- AE onset date (vs first administration)
  - AE start date ≥ date of first administration: AE start date – date of first administration + 1 day

- AE start date < date of first administration: AE start date – date of first administration

AE onset date will be computed only if the AE start date is fully known.

- AE duration (days)=
  - AE end date – AE start date +1
  - Study discontinuation date – AE start date + 1 day (when the AE is not resolved at the end of the study). In this case, the duration will be presented as “>x days”

AE duration will be computed only if the start and end date are fully known.

- AE rate per 100 patients’ year of follow-up (PYFU) defined as  $100 * \frac{\text{number of events}}{\text{sum of follow-up time}}$  during which an event is considered treatment-emergent of all participants per treatment arm expressed in years (ie, divided by 365.25) during the period. AE rate will be derived for DBTP and DBTP and safety follow-up combined as defined in section 5.2.

The following definitions will be used for the analysis of adverse events (AEs):

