### **IVIg Dependency Period (IVDP)**

Participants whose IVIg dependency is uncertain based on the MCC will enter an IVIg dependency period to assess the impact of a delayed IVIg administration on GS and/or motor function. Participants will receive IVIg following a delayed administration schedule compared to their stable IVIg regimen interval. Frequency of visits during the IVDP is:

- Participants receiving IVIg every 2 weeks will extend the interval to 4 weeks
- Participants receiving IVIg every 3 weeks will extend the interval to 6 weeks
- Participants receiving IVIg every 4 weeks will extend the interval to 8 weeks
- Participants receiving IVIg every 5 weeks will extend the interval to 10 weeks

Participants will have an earlier visit than planned during the IVDP if a participant demonstrates a clinically meaningful deterioration between the scheduled visits of the IVDP. [REDACTED]

[REDACTED]

[REDACTED]

[REDACTED]

The IVDP will last up to 15 weeks (105 days) depending on the IVIg dose frequency.

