## 4 ANALYSIS SETS

### 4.1 Analysis Set Definitions

The following data sets will be used for the statistical analysis:

**Enrolled (ENR) Set:** all participants who signed an informed consent to participate to the trial

Note: Having signed an informed consent is defined as having a complete date for consent signature in the database.

**Safety (SAF) Set:** All enrolled participants who were randomized and received at least 1 dose, or part thereof, of IMP (ARGX-117 or placebo). Participants will be analyzed according to the treatment they received.

**PK Set:** All participants in the SAF and for whom at least 1 post dose serum PK concentration is available, excluding placebo participants.

**PD Set:** All participants in the SAF for whom at least 1 post-baseline value for PD parameter (including free C2, total C2 and CH50) is available

The SAF set will be used to analyze the primary safety analysis. The SAF will be used to analyze efficacy endpoints.

For analyses performed on the SAF, PK and PD sets, the actual treatment arm will be considered.

[REDACTED]

If a treatment switch or misallocation occurred, sensitivity analyses might be performed.

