Descriptive statistics for immunogenicity titer values will include the number of observed values, arithmetic mean, SE, 95% CI, median, Q1, Q3, minimum, maximum, the GM, and geometric CV%.

Mean, 95% CI, Q1, Q3, and median will be presented with one more decimal place than the measured values. SE and SD will be presented with 2 more decimal places than the measured values. Minimum and maximum will be presented with the same number of decimal places as the measured values.

For event-type safety data, the number and percentage of participants with an event will be shown. The denominator will be all participants in the analysis set per treatment arm.

For cross-tabulations, the denominator will be the number of participants in the analysis set per treatment arm. For tables where results are shown by analysis visit, the denominator will be the number of participants in the analysis set per treatment arm and analysis visit. Missing values will not be included in the denominator count when computing percentages. Percentages will be presented with 1 decimal place.

If a participant is re-screened, only data from the last screening will be displayed.

Data from the SFU period will be listed only.

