### Summary Tables of AE by SOC and PT

Summary tables will be presented by treatment group. The selected TEAEs listed above, excluding fatal events and those leading to interruption of IMP, will also be summarized in terms of participant incidence rates and number of events by SOC and PT during the DBTP in the SAF set.

A summary table of TEAE by SOC and PT will be provided for during the DBTP and SAFFU periods combined in the SAF set. Note that in any tabulation, a participant will contribute only once to the count for a given adverse event (SOC or Preferred Term), regardless of the number of episodes that occurred.

All AEs will be listed, including pretreatment AEs.

The following by-participant listings will be presented in the SAF set:

- all adverse events
- treatment-emergent SAE
- TEAE leading to withdrawal of IMP
- TEAE Leading to Interruption of IMP
- treatment-emergent AESI
- TEAE leading to death

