- s A research sample will be collected during the IVIg monitoring period (visits IMV1-IMV3). This sample should be collected predose and postdose of the IVIg administration. This sample should be collected immediately after the end of the IVIg administration, regardless of the duration (after the last hour or day) of the administration.
- t IVIg will be administered during the IVIg dependency and IVMP at the time points scheduled. IVIg may be administered over several days according to the local standard of care. All IVIg administrations must occur within the specified visit windows.
- u Grip strength will be measured on-site at all study visits and monitored daily starting from the IVDP or IVMP.
- v Adverse events and concomitant medications/procedures will be monitored continuously from receipt of informed consent signature until the last study-related activity. All available vaccination history should be recorded.

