PHARMACODYNAMICS					
Listing	16.2.6.3.1	Pharmacodynamics: Free C2, Total C2 and CH50 data - PD Set		x	x
IMMUNOGENICITY					
Listing	16.2.6.4.1	Immunogenicity data: ADA against ARGX-117 - Safety Set			x
ADVERSE EVENTS					
Listing	16.2.6.7.1	All Adverse Events by Participant and by MedDRA SOC / PT and Verbatim SOC / PT - Safety Set	x		x
Listing	16.2.6.7.2	Serious Treatment Emergent Adverse Events by Participant and by MedDRA SOC/ PT and Verbatim Term - Safety Set	x		x
Listing	16.2.6.7.3	Treatment-Emergent Adverse Events Leading to Withdrawal of IMP by Participant and MedDRA SOC/ PT and Verbatim - Safety Set	x		x

Listing	16.2.6.7.4	Treatment-Emergent Adverse Events Leading to Interruption of IMP by Participant and MedDRA SOC/ PT and Verbatim - Safety Set			x
Listing	16.2.6.7.5	Treatment-Emergent Adverse Events of Special Interest by Participant and by MedDRA SOC / PT and Verbatim - Safety Set	x		x
Listing	16.2.6.7.6	Treatment-Emergent Adverse Events Leading to Death by Participant and by MedDRA SOC / PT and Verbatim-safety Set	x		x
LABORATORY					
Listing	16.2.8.1.1	Laboratory Results: Blood Chemistry Results for Participants with Post-Baseline Abnormalities or Toxicity Grade $\geq 1$ - Safety Set	x		x
Listing	16.2.8.1.2	Laboratory Results: Hematology Results for Participants with Post-Baseline Abnormalities or Toxicity Grade $\geq 1$ - Safety Set	x		x
Listing	16.2.8.1.3	Laboratory Results: Coagulation Results for Participants with Post-Baseline Abnormalities or Toxicity Grade $\geq 1$ - Safety Set	x		x
Listing	16.2.8.1.4	Laboratory Results: Urinalysis Results Postbaseline Abnormalities - Safety Set	x		x
Listing	16.2.8.1.5	Laboratory Results: Antinuclear Antibodies (ANA) and ENA autoantibodies - Results with ANA titer > 1:80 - Safety Set	x		x
Listing	16.2.8.1.6	Laboratory Results for participants entering into the Safety Follow- up period – Safety Set			
VITAL SIGNS					

Listing	16.2.8.2.1	Vital Signs Results for Participants with Post-Baseline Abnormalities - Safety Set	x		x
ECG					
Listing	16.2.8.3.1	12-lead ECG for Participants with Post-Baseline Abnormalities - ECG parameters - Safety Set	x		x
OTHER					
Listing	16.2.8.4.1	Suicidal Ideation for Participants with Abnormal Values [1] - Safety Set	x		x

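### Adverse events are collected from consent, but every adverse event table and listing is on the dosed Safety Set, so events in consented participants who are never dosed have no adverse event output

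*SAP*

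**What the plan says.** **Collection.** A footnote to the run-in schedule in SAP section 9.1 says: "Adverse events and concomitant medications/procedures will be monitored continuously from receipt of informed consent signature until the last study-related activity".

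**Analysis sets.** Section 4.1 defines the Enrolled Set as "all participants who signed an informed consent to participate to the trial". It defines the Safety Set as "All enrolled participants who were randomized and received at least 1 dose, or part thereof, of IMP (ARGX-117 or placebo").

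**AE outputs.** Section 6.4.1 opens with "All adverse events evaluations will be performed in the SAF set". Under the summary tables by SOC and PT it adds "All AEs will be listed, including pretreatment AEs", and the next sentence places the by-participant listings in the Safety Set. In section 9.2.2, Listing 16.2.6.7.1 carries the title "All Adverse Events by Participant and by MedDRA SOC / PT and Verbatim SOC / PT - Safety Set".

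**Periods before dosing.** For the IVIg dependency period (IVDP), section 2.1 says: "Participants will receive IVIg following a delayed administration schedule compared to their stable IVIg regimen interval". The IVIg monitoring period (IVMP) that follows keeps participants on their usual IVIg regimen. Under section 6.3.1, anyone who consents but is not randomised is a screen failure, including those who leave during the IVDP or IVMP.

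**Re-screening.** Section 6.2.1 says: "If a participant is re-screened, only data from the last screening will be displayed".

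**The concern.** The trial does something to some participants before any study drug is given. Those whose IVIg dependency is uncertain have their IVIg interval doubled in the IVDP, and section 2.1 itself foresees that some may deteriorate and need an earlier visit. A participant who has a serious event or dies at that stage will not be dosed, so that person cannot enter the Safety Set. The listings would then show pretreatment events only for people who went on to be dosed, and the events most likely to stop someone from reaching dosing would be absent.

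What is at stake is complete reporting of harms in consented participants, from data already in the database. A reader of the study report could take the all-AE listing to cover everyone who consented when it does not.

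**Working it through.** No sample size, power or event figure is involved. The check traces the analysis set of each AE output and then adds up the time before dosing.

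**1. Trace of AE outputs**

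| Output | Set in title | Events covered |
|---|---|---|
| Tables 14.3.1.1 to 14.3.1.17 | Safety Set | Treatment-emergent only |
| Tables 14.2.4.11 to 14.2.4.15 (AEs by antidrug antibody class) | Safety Set | Treatment-emergent only |
| Listing 16.2.6.7.1 | Safety Set | All AEs, including pretreatment |
| Listings 16.2.6.7.2 to 16.2.6.7.6 (serious, withdrawal, interruption, special interest, death) | Safety Set | Treatment-emergent only |

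Treatment-emergent means onset at or after the first study drug administration (Table 10). The number of AE outputs on the Enrolled Set, or on Enrolled minus Safety, is 0. A death before dosing is excluded from the death listing twice: the person is outside the set, and the event is not treatment-emergent.

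**2. Where the Enrolled Set is used**

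Tables 14.1.1, 14.1.3 and 14.1.7 cover disposition, country and site, and analysis sets. Listings 16.2.1.4, 16.2.2.2 and 16.2.2.3 cover analysis sets and eligibility. Listing 16.2.3.1 covers Enrolled minus Safety and is titled as a list of non-randomised participants; its columns are not shown. The Enrolled Set disposition table counts screen failures by period with reasons. The SAP does not say whether an AE is one of the reasons. If it is, a count gives no event term, grade, seriousness, relation to IVIg or outcome. The count of participants randomised but not dosed is placed in a Safety Set table, where it is zero by definition.

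**3. Time before dosing**

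Inputs are the visit days in Table 18, the 7 days from the final IVIg administration to the first study drug dose, and the rule that IMV1 is the next regular IVIg visit after IDV2.

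- IVMP = (day of IMV3 − 1) + 7. Every 2 weeks: 28 + 7 = 35 days. Every 3 weeks: 42 + 7 = 49. Every 4 weeks: 56 + 7 = 63. Every 5 weeks: 70 + 7 = 77. All four match section 2.1.
- Longest IVDP = (day of IDV2 − 1) + one usual interval. Every 5 weeks: 70 + 35 = 105 days, matching the stated 15 weeks.
- Shortest completed path: IVMP only, every 2 weeks = 35 days.
- Longest completed path: IVDP plus IVMP, every 5 weeks = 105 + 77 = 182 days.

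For comparison, the double-blind period is 16 × 7 = 112 days. The range is for nominal visit days and excludes screening (up to 28 days, or 42 if extended). A participant who leaves early has less time than this.

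**The case against.** The strongest case on the other side is that section 6.4.1 sets the Safety Set as its scope in its first line, and that the Safety Set is the right population for the primary objective, which compares ARGX-117 with placebo. People who were never dosed cannot inform that comparison. This stands, and the treatment-emergent tables should not move.

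Several stronger readings are tempting, and the SAP does not support them.

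- **That the plan contradicts itself on listing all AEs.** The sentence can be read within the scope of 6.4.1, as all AEs of Safety Set participants. It is loosely worded and invites a wider reading, but it is not a clear contradiction.
- **That the outputs give a biased estimate of run-in harm.** No planned output estimates an AE rate before dosing, so there is no estimate to bias. What is missing is listed data.
- **That such events can leave no trace at all.** An AE-driven exit may appear as a reason count in disposition.
- **That the IVMP is also a trial-imposed risk.** Participants stay on their usual regimen there. Only the IVDP delays IVIg, and only for those whose dependency is uncertain.
- **That 26 weeks is typical.** It is the maximum, for dosing every 5 weeks with both periods completed.
- **That the number affected can be estimated.** If 10% to 30% of enrolled participants were lost before dosing, reaching 48 dosed would leave 48/0.9 − 48 = 5.3 to 48/0.7 − 48 = 20.6 people outside the Safety Set. The loss rate is pure assumption, and the count would include people who failed at the screening visit and never entered the run-in.
- **That the re-screening rule discards a whole IVDP.** Section 5.2 defines screening as a period separate from the IVDP, and the SAP does not say whether re-screening can follow the IVDP.

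**Conclusion.** The gap is real. As planned, AEs, serious AEs and deaths in consented participants who are never dosed have no AE output. The finding rests on the analysis set definitions, the text of 6.4.1 and the output titles in Tables 24 and 25, and needs no assumed figure. It matters mainly for the IVDP, because the trial imposes the delay and a serious event there may be the reason for not dosing.

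The time concerned is 35 to 182 days for those who complete the periods, excluding screening. How many people are affected cannot be taken from the document. The effect of the re-screening rule is conditional on whether an earlier attempt can have recorded AEs. The gap concerns complete reporting of harms before dosing. It is not a flaw in the comparison of ARGX-117 with placebo.

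**What to change.** 1. Produce Listing 16.2.6.7.1 on the Enrolled Set, with a column for period of onset (screening, IVDP, IVMP, double-blind, safety follow-up).
2. Add one Enrolled Set listing of all serious and fatal AEs, not limited to treatment-emergent events.
3. Reword the opening line of 6.4.1 and the sentence on listing all AEs so that both state the set that applies to each output.
4. If re-screening can follow an attempt with recorded AEs, exempt AEs from the rule in section 6.2.1 that shows only the last screening.
5. Leave all treatment-emergent tables on the Safety Set.

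The cost is a short SAP wording change, one listing with a wider set and one short extra listing. The data are already collected, and no endpoint or treatment comparison changes.

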**Table 10 Adverse Event Definitions**

	Definition
Treatment-emergent adverse event (TEAE)	Treatment-emergent AEs are defined as AEs with onset on or after the first administration of IMP
Treatment Related AE	Any AE reported by the investigator as treatment related (ie, “Relationship to ARGX-117/Placebo= Related” in the CRF “Adverse event” page) and those of missing relationship.
IVIg Related AE	Any AE reported by the investigator as IVIg related (ie, “Relationship to IVIg treatment= Related” in the CRF “Adverse event” page) and those of missing relationship.
Procedure Related AE	Any AE reported by the investigator as procedure related (ie, “Relationship to any study procedure = Related”) and those of /missing relationship.
Serious Adverse Events (SAEs)	Any AE with “Is this a serious adverse event?” = Yes in the CRF “Adverse event” page.
Non serious Adverse Events	Any AE with “Is this a serious adverse event?” = No in the CRF “Adverse event” page.
Adverse Events Leading to Interruption of IMP	Any AE with “ARGX-117/Placebo interrupted?” = Yes in the CRF “Adverse event” page.
Adverse Events Leading to Permanent Treatment Discontinuation	Any AE with “ARGX-117/Placebo withdrawn” = Yes in the CRF “Adverse event” page.
Adverse Events Leading to Death	Any AE with fatal outcome or AE with NCI CTCAE grade = 5
Adverse Event of Special Interest	AESIs are defined as events with grade ≥ 3 and a PT that falls under the MedDRA SOC Infections and infestations.
Adverse Event of Hypersensitivity Reactions	Any AE with PT from SMQ (narrow) selection for hypersensitivity reaction
Adverse events of Anaphylactic Reaction	Any AE with PT from SMQ (narrow) selection for anaphylactic reaction
Adverse Events of Local Reactions	Any AE with MedDRA PT in the MedDRA High Level Group Term of administration site reactions, regardless of time of onset.

Summary tables of TEAEs will be presented for the DBTP (SAF set).

AE will also be allocated to the first period that is possible based on the available part of the AE start and stop date/time. If, for a participant not entering the safety follow-up period or LTE, an AE occurs following V14 or treatment discontinuation, then the AE will be counted in the DBTP.

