### Screening Period

All participants will begin with a screening period. The individual's eligibility to participate in the trial will be assessed. The diagnosis of MMN will be confirmed by the MMN Confirmation Committee (MCC) to be eligible. IVIg dependency will be assessed by the MCC as well.

Participants whose IVIg dependency is uncertain will enter an IVIg dependency period. Participants whose IVIg dependency is certain will enter directly in an IVIg monitoring period.

The screening period will occur for up to 28 days and may be extended by an additional 14 days to a total of 42 days with the written approval of the medical monitor.

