## 6.2.7 Missing, Unused, and Spurious Data

### 6.2.7.1 Adverse events missing dates

AEs will be considered treatment-emergent based on their start date/time.

Imputation of missing/partial AE dates/time will be performed only to identify treatment-emergent AEs. If the AE start date/time is incomplete or missing, the AE will be considered treatment-emergent unless the available part of the AE start or stop date/time provide evidence that the event did not occur following initiation of IMP. The following rules allow for an imputed start and stop date that adheres to this convention:

For partial or missing AE start date/time the following imputation will be applied:

1. If year is not missing and is after the year of first IMP dose:
  - a. If month is missing, then month will be imputed as January.
  - b. If day is missing, then day will be imputed as the first of the month.
2. If year is not missing and is the same as the year of the first IMP dose:
  - a. If month is missing, then impute the month as the month of the first dose date.
  - b. If day is missing, and the month is the same as the month of the first dose date, then impute day as the day of the first dose date.
  - c. If day is missing but month is after the month of first dose date, then impute day as the first day of the month.
3. If year is missing then impute the date of the first IMP administration.
4. If the start date is completely missing, but the AE is either ongoing or the stop date or imputed stop date (in case of partially missing stop date) is after the first dose date then impute the start date as the first dose date.
5. For any cases involving the rules above, if the AE stop date or imputed stop date (in case of partially missing stop date) is before the AE start date, then do not impute the AE start date and assume that the AE is treatment-emergent for the purpose of the analysis. Further, if the AE stop date or imputed AE stop date (in case of partially missing stop date) occurs prior to the first dose date, do not impute the AE start date, and assume that the AE is not treatment-emergent.

For partial or missing AE start time the following imputation will be applied:

1. If date or imputed date is the date of the of the first IMP dose, then the time will be the time of the IMP administration
2. If date or imputed date is different from the date of the of the first IMP dose, then time will be 00 h 00 min.

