For laboratory parameters with no toxicity grades results will be categorized according to reference ranges from the central laboratory using non imputed value and limits as:

Low if parameter result is < Lower Limit of Normal (LLN)

High if parameter result is > Upper Limit of Normal (ULN)

Normal if parameter value is within normal range ( $LLN \leq \text{result} \leq ULN$ )

Treatment-emergent out-of-range values are defined as laboratory values:

- with normal values at baseline and low or high value at any post baseline visit, or
- with low values at baseline and high at any post baseline visit, or
- with high values at baseline and low at any post baseline visit.

If baseline is missing, any post-baseline abnormality will be considered treatment emergent.

For parameters with toxicity grades (Table 12), Treatment-emergent toxicity grade values are defined as laboratory values with higher grade post-baseline compared to the grade at baseline. If baseline is missing any postbaseline toxicity will be considered treatment-emergent.

The CTCAE Version 5.0 will be used as the basis for toxicity grading. CTCAE grades will be programmatically derived as described in the Table 12 when applicable.

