**Table 14 Low, Normal and High Ranges for ECG parameters (Heart rate, PR and QRS)**

Parameters	Range		
	Low	Normal	High
Heart rate (beats/min)	< 40	40 -100	> 100
PR (ms)	< 120	120 – 220	> 220
QRS (ms)	< NA	0-120	> 120

NA: Not Applicable

Treatment-emergent out-of-range values are defined as follows :

- with normal values at baseline and low or high value at any post baseline visit, or
- with low values at baseline and high at any post baseline visit, or
- with high values at baseline and low at any post baseline visit.

If baseline is missing any postbaseline abnormality will be considered treatment-emergent.

For QTcB and QTcF (ms), the following categories will be derived:

- For the actual values: ≤ 450 (normal), ]450 ;480], ]480 ; 500], and > 500
- For the change from baseline: ≤ 30 (normal), ]30;60] and > 60.

For QTcB and QTcF, a treatment-emergent abnormality is defined as any postbaseline abnormality which was not present at baseline or which worsened following baseline (eg, QTcF ]450; 480] ms at baseline and >500 ms postbaseline). If baseline is missing any postbaseline abnormality will be considered treatment-emergent.

ECG parameters (heart rate, PR, QRS, QT, QTcB and QTcF intervals) will be summarized using actual value and change from baseline at each visit/time point by treatment group and overall in the SAF set on the DBTP.

For heart rate, PR and QRS, shift tables will also be created to summarize the number and proportion of participants with shifts from baseline category to “Low”, “Normal”, “High”, treatment-emergent by treatment group and visit . Shift tables from baseline to worst post DBTP baseline category will also be presented. In case of low and high post- baseline values, a category ‘low + high’ will be defined.

All ECG data for participants with post baseline abnormalities will be listed.

For QTc, shift tables will be created to summarize the number and proportion of participants with shifts from baseline to all visits according to the abnormality by treatment group and visit. Shift tables from baseline to worst post DBTP baseline abnormality will also be presented. Numbers and cumulative numbers of participants with treatment-emergent abnormalities will also be shown.

Abnormalities of QTc changes will be summarized at each post-baseline analysis visit and at the worst-post-Baseline analysis visit. Number and Cumulative numbers of participants with change abnormalities will also be shown.

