Grip strength a		X	Continuous Monitoring				
MMN-RODS		X	X	X	X	X	X
mMRC		X	X	X	X	X	X
9-HPT		X	X	X	X	X	X
HRPQ					X	X	X
EQ-5D-5L					X	X	X
CAP-PRI					X	X	X
FSS					X	X	X

9-HPT=9-Hole Peg Test; ANA=antinuclear antibody; BMI=body mass index; CAP-PRI=chronic acquired polyneuropathy patient-reported index; C-SSRS=Columbia- suicide severity rating scale; DBTP=double-blinded treatment period; dsDNA=double stranded DNA; ECG=electrocardiogram; ENA=extractable nuclear antigen antibodies; EQ-5D-5L=Euro-Quality of Life 5 Dimensions 5 Levels; FSH=follicle-stimulating hormone; FSS=fatigue severity scale; ██████████  
 HRPQ=Health-Related Productivity Questionnaire; IDV=IVIg dependency visit; IMP=investigational medicinal product; IMV=IVIg monitoring visit; INR=international normalized ratio; IVDP=IVIg dependency period; IVIg=intravenous immunoglobulin; IVMP=IVIg monitoring period; MCC=MMN Confirmation Committee; MMN=multifocal motor neuropathy; MMN-RODS=Rasch-built overall disability scale for MMN; mMRC=modified Medical Research Council; NAb=neutralizing antibodies; ██████████  
 PD=pharmacodynamic(s); PE=physical examination; PHQ-9=patient health questionnaire 9 depression questionnaire; Q=every; SCN=screening period; SIB=suicidal ideation and behavior; SLE=systemic lupus erythematosus; SNP=single nucleotide polymorphism; TSQM=Treatment Satisfaction 14-item Questionnaire for Medication

Note: All assessments will be performed before IVIg administration unless otherwise specified.

\* **For Germany only:** A SARS-CoV-2 rapid antigen test must be completed or a negative rapid antigen test not older than 48 hours (depending on local requirements) must be presented upon site entry for each visit. The antigen test must be negative before the visit can begin. Rapid antigen testing will only be mandatory if required locally.

- a The screening period is 1 to 28 days before the IVMP or the IVDP. The scheduled time of visit is variable based on the participant's IVIg dose regimen retrieved from their medical record (inclusion criterion 5.1a). The screening period may be extended by an additional 14 days to a total of 42 days with the written approval of the medical monitor.
- b The IVDP, if applicable, occurs up to 15 weeks (105 days) before the IVMP.
- c The IVMP occurs up to 11 weeks before day 1 of the DBTP.
- d IDV1 will coincide with the participant's regularly scheduled IVIg administration.

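### A TEAE is defined by onset date alone, so an AE that starts before the first IMP dose and worsens afterwards goes uncounted unless the worsening is entered as a new AE

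*SAP*

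**What the plan says.** Table 10 in Section 6.4.1 gives the definition: "Treatment-emergent AEs are defined as AEs with onset on or after the first administration of IMP". Section 6.2.7.1 gives the classification rule: "AEs will be considered treatment-emergent based on their start date/time". For period allocation, the text after Table 10 adds: "AE will also be allocated to the first period that is possible based on the available part of the AE start and stop date/time". None of the three deals with an AE that is already present at the first dose and then becomes more severe or serious.

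Collection starts long before dosing. A footnote to the first schedule of activities in Section 9.1 reads: "Adverse events and concomitant medications/procedures will be monitored continuously from receipt of informed consent signature until the last study-related activity".

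The overview and SOC/PT summaries in Section 6.4.1 are restricted to TEAEs. So are the dedicated listings for SAEs, AESIs, IMP withdrawal, IMP interruption and death. AEs from before treatment appear only in the listing of all AEs.

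Two other kinds of safety data are treated differently. For graded laboratory parameters, Section 6.4.2 says: "Treatment-emergent toxicity grade values are defined as laboratory values with higher grade post-baseline compared to the grade at baseline". For QTcB and QTcF, Section 6.4.4 counts "any postbaseline abnormality which was not present at baseline or which worsened following baseline".

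**The concern.** Safety is the primary objective and AEs are a primary endpoint. Take a grade 1 infection that starts in the IVIg monitoring period, reaches grade 3 after dosing and leads to IMP withdrawal. If it stays one record with its pre-dose start date, it is not a TEAE. It then misses the grade 3 or higher, AESI and withdrawal tables, and the AESI and withdrawal listings.

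The rule can only lower the count of on-treatment harm. The run-in is long and eventful: repeated IVIg infusions for everyone and, for some, deliberately delayed IVIg. AEs still ongoing at the first dose are therefore plausible. Arms are small, so one participant matters: 1/16 = 6.3 percentage points in an arm of 16, and 1/8 = 12.5 points in a placebo group of 8 (24 participants randomised 2:1).

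**Working it through.** **Inputs, all from the SAP**
- Screening, Section 2.1: "The screening period will occur for up to 28 days and may be extended by an additional 14 days to a total of 42 days". The Section 9.1 footnote gives the lower end: "The screening period is 1 to 28 days before the IVMP or the IVDP".
- IVIg dependency period (IVDP), Section 2.1: only for participants with uncertain dependency, up to 105 days.
- IVIg monitoring period (IVMP), Section 2.1: 35, 49, 63 or 77 days for IVIg every 2, 3, 4 or 5 weeks.
- Double-blind treatment period (DBTP): 16 weeks = 112 days.

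**Reproducing the plan's own figures**
- IVMP = two IVIg intervals + 7 days: 28 + 7 = 35, 42 + 7 = 49, 56 + 7 = 63, 70 + 7 = 77. All four match.
- IVDP maximum = doubled 5-week interval + one regular interval = 70 + 35 = 105 days. Matches.
- Minimum trial duration = 28 + 35 + 112 = 175 days = 25 weeks. Matches the stated 25 weeks.

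**Length of AE collection before first IMP**

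| Case | Days | Weeks | Share of collection time up to day 112 of DBTP |
|---|---|---|---|
| Shortest IVMP alone | 35 | 5.0 | 35/147 = 24% |
| 28-day screening + shortest IVMP | 63 | 9.0 | 63/175 = 36% |
| Longest without an IVDP: 42 + 77 | 119 | 17.0 | 119/231 = 52% |
| Longest: 42 + 105 + 77 | 224 | 32.0 | 224/336 = 67% |

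Adding the one-day minimum screening to the first row gives 36 days, or 5.1 weeks.

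**Passing cases through the rules**
1. *Known onset in the IVMP, grade 1, then grade 3 in the DBTP, one record.* The start date precedes first IMP, so Table 10 and 6.2.7.1 both say not treatment-emergent. The event is allocated to the IVMP. It appears in the all-AE listing only.
2. *Same event, with the worsening entered as a new record dated in the DBTP.* The new record starts after first IMP and is a TEAE. Nothing is lost.
3. *Ongoing event with a completely missing start date.* 6.2.7.1 imputes the first dose date and counts it as a TEAE. The exclusion therefore reaches only AEs whose dates show pre-dose onset.

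**How far the comparison with other safety data goes**
- Graded laboratory parameters and QTc count worsening from an already abnormal baseline.
- Ungraded laboratory parameters, vital signs, ECG heart rate, PR and QRS need a change of category: normal to low or high, low to high, or high to low. A high value that becomes higher is not treatment-emergent.

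**The case against.** The strongest counter-argument is that the loss depends on a recording rule that is not visible. If a change in grade or seriousness is entered as a new AE, Table 10 already captures it, and such rules commonly sit in the protocol or CRF instructions. This stands, and it makes the consequence conditional.

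Nor is there a strict contradiction. Table 10 and 6.2.7.1 agree with each other. Laboratory and ECG values are repeated measurements against a baseline, while AEs are dated records. A reader might infer that the plan counts worsening for laboratory data in general and breaks that principle only for AEs. The text does not support this, because only graded parameters and QTc follow it.

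The affected events are also not invisible. They are in the all-AE listing, reasons for discontinuation are tabulated in the disposition summaries (Section 6.3.1), and MMN deterioration is analysed as relapse and IVIg retreatment (Section 6.5.1.1). These outputs soften the gap but do not replace a correct TEAE count.

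A reader might also want a number of missed events. Assuming 1 to 2 pre-dose AEs per participant, 20 to 30% ongoing at first dose and 5 to 15% of those worsening, 48 participants give 48 × 1 × 0.20 × 0.05 = 0.5 to 48 × 2 × 0.30 × 0.15 = 4.3 events. None of those rates is in the SAP, so this shows only how wide the guess is. Likewise, nothing shows that infections or neuropathy-related events are the ones affected, or that one arm loses more events than another. The rule is the same for active and placebo.

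Finally, the 32-week end needs an extended screening, an IVDP and 5-weekly IVIg, all at their maximum.

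**Conclusion.** The point holds in conditional form. The onset-only rule is stated twice and governs the main outputs of a primary endpoint. AEs with documented onset in the roughly 5 to 32 weeks before first IMP that increase in grade or become serious on treatment would be left out of the TEAE tables and the dedicated listings, unless the worsening is a new AE record with its own start date.

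The window follows from the SAP's nominal period lengths. It would be slightly longer where IVIg is given over several days, as the SAP allows. The number of events cannot be derived from the document, and no direction of between-arm bias is claimed. To say flatly that every such event is lost would go beyond what the SAP shows. This is a cheap improvement to the completeness of the on-treatment AE count.

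**What to change.** In Table 10 and Section 6.2.7.1, extend the definition to include: *or onset before the first IMP administration with an increase in CTCAE grade, or becoming serious, on or after it*. Use the date of worsening for period allocation. If worsening is already entered as a new record, the clause changes nothing, and a sentence saying so would be enough.

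If the CRF holds only the worst grade per AE, the clause cannot be programmed directly. In that case, take the AEs ongoing at first dose that are grade 3 or higher, serious, or led to IMP interruption or withdrawal. Flag them by a prespecified programmed rule or by a reviewer blind to treatment, and show them in a separate row of Table 14.3.1.1. Open case-by-case review is not suitable, because Section 2.1 has both cohorts unblinded by the second interim analysis.

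The cost is one sentence in two places and one flag in the AE dataset. TEAE counts may rise slightly and differ from the interim outputs, which the study report should explain.
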